3.1 STUDY OUTCOME MEASURES

Phase 1:

Primary Outcome Measures

- Similar signal to noise ratios (SNR) for MR spectroscopy at 1.5Tesla and 3Tesla, using clinical acceptable scan duration at 1.5 Tesla.

Phase 2:

Primary outcome measures

- Mean (SD) of thalamic NAA level in babies treated with Epo and Darbe when compared with untreated infants.

Secondary outcome measures

- Number of babies in whom thalamic NAA level could be accurately quantified in 3Telsa and 1.5Tesla MR scanners.

4. PARTICIPANT ENTRY

4.1 INCLUSION CRITERIA

Phase 1

Adults >18 years old.

Phase 2

All babies aged ≤ 24 hours, ≥ 36 weeks with a birth-weight >1.8 kg with clinical evidence of encephalopathy (mild, moderate or severe) within 6 hours of birth, along with evidence of an intra-partum asphyxia insult and where cooling therapy encephalopathy within 6 hours of age as a part of standard clinical care, with an intention of continuing for 72 hours.

4.2 EXCLUSION CRITERIA

Phase 1:

1. Adults with existing disease.
2. Adults with metal implant fitted, such as a pacemaker or artificial joint
3. Pregnancy

Phase 2:

1. Babies without encephalopathy.
2. Major life-threatening congenital malformation.
3. Concomitant participation in other research projects

4.3 WITHDRAWAL CRITERIA

Phase 1:

Withdrawal of consent

Phase 2:

Withdrawal of parent or physician consent

5. ADVERSE EVENTS

5.1 DEFINITIONS

Adverse Event (AE): any untoward medical occurrence in a patient or clinical study subject.

Serious Adverse Event (SAE): any untoward and unexpected medical occurrence or effect that:

- **Results in death**
- **Is life-threatening** – *refers to an event in which the subject was at risk of death at the time of the event; it does not refer to an event which hypothetically might have caused death if it were more severe*
- **Requires hospitalisation, or prolongation of existing inpatients' hospitalisation**
- **Results in persistent or significant disability or incapacity**
- **Is a congenital anomaly or birth defect**

Medical judgement should be exercised in deciding whether an AE is serious in other situations. Important AEs that are not immediately life-threatening or do not result in death or hospitalisation

but may jeopardise the subject or may require intervention to prevent one of the other outcomes listed in the definition above, should also be considered serious.

5.3 REPORTING PROCEDURES

All adverse events should be reported. Depending on the nature of the event the reporting procedures below should be followed. Any questions concerning adverse event reporting should be directed to the Chief Investigator in the first instance.

5.3.1 Non serious AEs

All such events, whether expected or not, should be recorded.

5.3.2 Serious AEs

Prespecified serious adverse events (SAEs) are:

- Systemic hypertension requiring anti-hypertensive therapy
- Polycythemia
- Disseminated intravascular coagulation (clinical bleeding/oozing requiring transfusion of blood product)
- Major venous or arterial thrombosis not related to a central line
- Pulmonary hypertension treated with inhaled nitric oxide or extracorporeal life support
- Intracranial hemorrhage visualized on head ultrasound or MRI T1 or T2 sequences
- Cardiopulmonary arrest not secondary to ETT obstruction or other mechanical issue
- Death

An SAE form should be completed and faxed to the Chief Investigator within 24 hours. However, relapse and death due to Neonatal Encephalopathy, and hospitalisations for elective treatment of a pre-existing condition do not need reporting as SAEs.

All SAEs should be reported to the **West of Scotland Research Ethics Committee** where in the opinion of the Chief Investigator, the event was:

- 'related', ie resulted from the administration of any of the research procedures; and
- 'unexpected', ie an event that is not listed in the protocol as an expected occurrence

Reports of related and unexpected SAEs should be submitted within 15 days of the Chief Investigator becoming aware of the event, using the NRES SAE form for non-IMP studies. The Chief Investigator must also notify the Sponsor of all SAEs.

Local investigators should report any SAEs as required by their Local Research Ethics Committee, Sponsor and/or Research & Development Office.

Contact details for reporting SAEs

[contact]

CI email (and contact details below)

[contact], attention [name]

Please send SAE forms to: [contact]

[contact] (Mon to Fri 09.00 – 17.00)

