3.1 STUDY OUTCOME MEASURES	10
4. PARTICIPANT ENTRY	11
4.1 INCLUSION CRITERIA	11
4.2 EXCLUSION CRITERIA	11
4.3 WITHDRAWAL CRITERIA	11
5. ADVERSE EVENTS	11
5.1 DEFINITIONS	11
5.3 REPORTING PROCEDURES	12
6. ASSESSMENT AND FOLLOW-UP	13
7. STATISTICS AND DATA ANALYSIS	13
8. REGULATORY ISSUES	13
8.1 ETHICS APPROVAL	13
8.2 CONSENT	14
8.3 CONFIDENTIALITY	14
8.4 INDEMNITY	14
8.5 SPONSOR	14
8.6 FUNDING	14
8.7 AUDITS	14
9. STUDY MANAGEMENT	15
10. PUBLICATION POLICY	15
11. REFERENCES	15
12. APPENDICES	17

GLOSSARY OF ABBREVIATIONS

EPO	Erythropoietin
DARBE	Darbepoetin alfa
NAA	N-acetylaspartate
MR	Magnetic resonance
HIE	Hypoxic Ischemic Encephalopathy
NE	Neonatal encephalopathy
MRS	Magnetic resonance spectroscopy
LAC	Lactate
U	Units
KG	Kilograms
LMIC	Low and middle-income countries
µG	Micrograms
IV	Intravenous
SNR	Signal to Noise Ratios
EEG	Electroencephalography

STUDY SUMMARY

TITLE Erythropoietin and Darbepoetin in Neonatal Encephalopathy (EDEN) study

DESIGN 3 arm open label pilot randomised controlled trial.

AIMS To examine the physiological effects of erythropoietin (Epo) and Darbepoetin alfa (Darbe) therapy on proton magnetic resonance spectroscopy thalamic N-acetylaspartate (NAA) level in babies with neonatal encephalopathy undergoing cooling therapy.

OUTCOME MEASURES

Phase 1

Primary outcome

Optimization of the signal to noise ratios (SNR) for MR spectroscopy at 1.5Tesla and 3Tesla, using clinical acceptable scan duration at 1.5 Tesla.

Phase 2

Primary outcome

Mean (SD) of thalamic NAA level in babies treated with Epo and Darbe when compared with untreated infants for predicting adverse neurodevelopment.

Secondary outcome

Number of babies in whom thalamic NAA level could be accurately quantified in 3Telsa and 1.5Tesla MR scanners.

POPULATION 20 Adult Healthy Volunteers
220 newborns with hypoxic ischemic encephalopathy.

ELIGIBILITY

Phase 1: Adults

Inclusion Criteria

1. >18 years old.

Exclusion Criteria

1. Adults with disease.
2. Adults with metal implant fitted, such as a pacemaker or artificial joint
3. Pregnancy.

Phase 2: Infants

Inclusion Criteria

1. Age \leq 24 hours
2. Birth-weight $>$ 1.8 kg
3. Gestation \geq 36 weeks
4. Need for continued resuscitation at 10 minutes after birth and/or 10 minutes Apgar score $<$ 6

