Erythropoietin stimulating Agents (ESA) are glycoprotein regulating red blood cell production and are used to treat anaemia due to chemotherapy, kidney disease, major surgery, or certain treatments in HIV in adult and children.

Most complications of ESAs have been derived from studies in adults. The more common complications of prolonged ESA treatment in adults and children are arthralgia, embolism and thrombosis, headaches, flu-like symptoms, hypertension, skin reactions, stroke, hypertensive crisis, respiratory tract congestion, seizure, thrombocytosis and pure red cell aplasia¹⁵.

Several individual studies have shown a potential trend associating ESA use with increased cancer progression¹⁶⁻¹⁸. Apro et al¹⁹ in systematic review concludes that the balance of current evidence does not support an effect of ESAs on stimulating tumor progression in adults receiving chemotherapy and treated for a minimum of 4 weeks and up to 12 months. A Cochrane review by Tonia et al²⁰ showed that the available data are insufficient to evaluate the effect of ESAs on tumour response.

EPOETIN ZETA	DARBEPOETIN ALPHA
Common or very common Asthenia; dizziness	Common or very common Hypersensitivity; oedema
Uncommon Intracranial haemorrhage	
Rare or very rare Angioedema	
Frequency not known Aneurysm; cerebrovascular insufficiency; hypertensive encephalopathy; myocardial infarction; myocardial ischaemia	

Table 1. Specific complications from Epoetin Zeta and Darbeпоetin Alpha in children.²¹

However, these adverse effects have not been reported in Epo- or Darbe-treated neonates. In clinical trials that evaluated possible undesired side-effects from epo and darbe treatment in term infants found no difference in adverse outcomes or complications, compared to control group, as outlined in Appendix 1. Erythropoietin dosing regimens in neonates for intravenous infusion vary between 250IU/kg to 2500IU/kg, 3 to 7 doses for a maximum of two weeks (Appendix 1). In adults, Epo dosing regimens vary between 50-600units/kg 3 times weekly for a minimum of 4 weeks¹⁵.

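### The prespecified thrombosis event leaves out line-related clots, on a judgement that unblinded staff make after randomisation; count every major clot and flag line relation instead

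*Protocol*

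**What the plan says.** Section 5.3.2 of the protocol gives eight prespecified serious adverse events. The thrombosis item reads "Major venous or arterial thrombosis not related to a central line". It is the list's thrombosis item, and its wording takes out clots attributed to a central line.

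Section 1.1, on the safety profile of the two drugs, says: "The more common complications of prolonged ESA treatment in adults and children are arthralgia, embolism and thrombosis". The same section adds that such effects have not been reported in treated neonates.

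The Study Summary describes the trial as open label with three arms. Under Study Design, the arms receive five daily intravenous doses of erythropoietin, one intravenous dose of darbepoetin, or cooling alone.

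The wider safety net is in sections 5.1, 5.3 and 5.3.1. An adverse event is "any untoward medical occurrence in a patient or clinical study subject". All adverse events are to be reported, and non-serious ones recorded whether expected or not. An event can also be serious on general grounds, for example "Requires hospitalisation, or prolongation of existing inpatients" (section 5.1), but that definition also requires the event to be unexpected.

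**The concern.** Thrombosis is one of the drug-class risks that the protocol itself names, so its prespecified event should catch any major clot that the drug could have provoked. A line and a drug that promotes clotting are not competing explanations: a clot at a line may still owe something to the drug. The item nevertheless asks staff to choose, and drops the clot if they choose the line.

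That choice is made after randomisation by people who know the allocation. The protocol gives no criterion for calling a clot line-related. If staff attribute clots differently in treated and untreated infants, the listed counts are no longer comparable between arms, and the direction of the distortion is unknown.

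The trial is meant to give a go or no-go signal for a later trial (section 1.1, benefits of the study). A thrombosis count that depends on unblinded attribution serves that purpose poorly.

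**Working it through.** **1. The plan's own figure.** The protocol states no figure for safety events. Its only reproducible design figure is the primary sample size in section 7: SD 0.8, difference 0.5, power 90%, significance 0.017. The standardised difference is 0.5/0.8 = 0.625. A two-sample t-test with two-sided alpha 0.017 needs 70.34 per group, rounded up to the stated 71. Then 3 × 71 = 213, raised to 220, and 220/3 is about 73 per arm if allocation is equal (assumed; the ratio is not stated). This supplies the arm size below and nothing more.

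**2. Where a major line-related clot goes.**
- Prespecified list (5.3.2): excluded.
- General serious criteria (5.1): it may qualify, for example if life-threatening or if it prolongs the stay. The requirement that a serious event be unexpected gives a site a reason not to use this route if it regards line clots as expected.
- Adverse event records (5.3, 5.3.1): included.

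So the clot leaves the prespecified list but stays in the safety data.

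**3. Illustration, equal attribution in both arms.** All rates are assumed. Let true major thrombosis be 2% (control) and 8% (one drug arm), and let a share *s* be classed as line-related. The listed rate is p × (1 − s). Power is for two proportions, 73 per arm, two-sided 0.05; the approximation is crude at such small counts.

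| s | Listed rates | Expected events per 73 | Power |
|---|---|---|---|
| 0 | 2% vs 8% | 1.46 vs 5.84 | 38% |
| 50% | 1% vs 4% | 0.73 vs 2.92 | 21% |
| 80% | 0.4% vs 1.6% | 0.29 vs 1.17 | 11% |
| 90% | 0.2% vs 0.8% | 0.15 vs 0.58 | 7% |

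The ratio stays at 4.0, while the difference falls from 6 points to 3, 1.2 and 0.6. Three studies summarised in Appendix 1 mention thrombosis and none reports a case put down to the drug, so 8% is a deliberately high assumption.

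**4. Illustration, unequal attribution.** Same true rates, ratio 4.0.
- 50% of control clots and 80% of drug clots classed as line-related: 2% × 0.5 = 1.0% and 8% × 0.2 = 1.6%, ratio 1.6.
- The reverse: 2% × 0.2 = 0.4% and 8% × 0.5 = 4.0%, ratio 10.

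The distortion can go either way.

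**5. Onset, a secondary matter.** No listed event carries an onset condition, and infants are randomised up to 24 hours of age. If a share *b* of each arm already has an event, the counted rate is b + (1 − b)p. With assumed p of 5% and 15% and b = 20%, this gives 0.20 + 0.80 × 0.05 = 24% and 0.20 + 0.80 × 0.15 = 32%. The ratio falls from 3.0 to 1.33, the difference from 10 to 8 points, and power from 52% to 19%. If p is equal in both arms, the counted rates are equal too, so prior events dilute a real contrast but do not create a false one.

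**The case against.** **Excluding line clots is a defensible choice for specificity.** If line use did differ by arm, counting line clots would mix a line effect into the drug contrast. This is a fair point, and it is why the line-related field is needed. With the field, the narrower count stays available; with the exclusion, the prespecified list can show only one of the two.

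**The clots are not lost.** This stands. A reader might infer that a thrombotic effect is hidden, but sections 5.3 and 5.3.1 rule that out. The loss is from the prespecified list and possibly from expedited serious reporting.

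**Line exposure is not shown to differ by arm.** This also stands. A reader might infer from five, one or no intravenous doses that it does. Study Design says only that the route is intravenous. It does not say that a central line is used, or that dosing decides who has one.

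**The background sentence concerns prolonged treatment in adults and children, and the protocol reports no such effects in neonates.** True, and it suggests low rates. It is not a reason to narrow the item meant to detect them.

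**The list is a reporting trigger, not an endpoint.** Section 3.1 names no safety outcome, and the protocol sets no between-arm analysis of the list. A reader should therefore not call it the trial's only safety comparison.

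**An onset rule belongs elsewhere.** Events such as "Pulmonary hypertension treated with inhaled nitric oxide or extracorporeal life support" or "Disseminated intravascular coagulation (clinical bleeding/oozing requiring transfusion of blood product" could precede randomisation, and a reader might treat the missing rule as a flaw in its own right. A rule on which events count as treatment-emergent is commonly set in the analysis plan or on the case report form, neither of which is shown. That reading is not supported.

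**Conclusion.** The point holds for the thrombosis item. Its wording removes line-related clots from the prespecified list, although thrombosis is a risk that the protocol names for this drug class, and it makes the count depend on attribution by staff who know the arm. The count can lose drug-related clots and could do so unevenly. That it does so, or in which direction, is not shown.

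The size cannot be stated from the document. The figures above rest on assumed event rates, assumed line-related shares and equal allocation. Even with every clot counted, power is only 38% in a favourable example, so the gain is a cleaner and more complete count rather than a well-powered test.

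For haemorrhage, defined as "Intracranial hemorrhage visualized on head ultrasound or MRI T1 or T2 sequences", nothing is excluded. At most, bleeds that predate the drug dilute the contrast, so a reader should not extend the thrombosis criticism to it.

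**What to change.** In section 5.3.2, remove the central-line exclusion so that every major venous or arterial thrombosis is reported as a prespecified event. Add a line-related yes/no field to the form as a descriptor, and show both counts by arm: all major clots, and those not attributed to a line.

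As a minor accompaniment, record for each listed event whether it began before or after randomisation. Randomisation is the one time point that all three arms share. Keep haemorrhage first seen on the MRI at 1 to 2 weeks in the arm comparison, with its onset flagged as unknown; setting those cases aside would discard signal.

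The cost is a wording change, two form fields and a few extra serious-event forms for clots that are purely line-related. No sample size or assessment changes.

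### Section 5.3.2 lists every death as a serious adverse event, then exempts deaths attributed to the disease that every Phase 2 baby has

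*Protocol*

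**What the plan says.** Four parts of the protocol bear on how a death is reported.

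- **Section 5.1** defines an SAE as "any untoward and unexpected medical occurrence or effect that" meets one of several outcomes. The first of these is "Results in death".
- **Section 5.3** opens with a general rule: "All adverse events should be reported".
- **Section 5.3.2** introduces a list with "Prespecified serious adverse events (SAEs) are". The last item is death, with no qualification by cause. The rules that follow are "An SAE form should be completed and faxed to the Chief Investigator within 24 hours" and, further down, "The Chief Investigator must also notify the Sponsor of all SAEs".
- **Section 5.3.2, directly after the 24-hour rule**, says that "relapse and death due to Neonatal Encephalopathy, and hospitalisations for elective treatment of a pre-existing condition do not need reporting as SAEs".

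Elsewhere, the Study Summary describes the trial as open label with three arms. Section 4.1 requires clinical evidence of encephalopathy in Phase 2, and section 4.2 excludes babies without it. Section 6.1 counts death in the adverse outcome at 18 to 24 months. Section 9 says that an independent Data Monitoring Committee will be appointed.

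**The concern.** The same section says both that death is an SAE and that death from the trial's own disease need not be reported as one. Exemptions for disease-related death usually assume that such deaths can be told apart from others. Here every treated baby has the disease, so the exemption depends on a judgement about cause, made at the site by clinicians who know the arm.

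Two things are at stake. The first is timing: a death attributed to encephalopathy need not reach the Chief Investigator within 24 hours, nor the Sponsor through the SAE route. The second is comparability: if clinicians attribute cause differently for babies given a study drug and babies who were only cooled, the count of reported deaths by arm is no longer a fair comparison, even if true mortality is equal. A count of all deaths by arm needs no such judgement.

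**Working it through.** There is no stated figure to reproduce, because the point is about text. I compared the passages first and then sized the consequence.

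**Step 1. Follow one death under each rule.**

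| Route | If the list governs | If the exemption governs and the death is attributed to encephalopathy |
|---|---|---|
| SAE form to the Chief Investigator in 24 hours (5.3.2) | Required | Not required |
| Sponsor told (5.3.2) | Required | Not required |
| Ethics committee in 15 days (5.3.2) | Only if related and unexpected | Not sent |
| General adverse event reporting (5.3) | Applies | Applies, with no time limit given |
| 18 to 24 month outcome (6.1) | Counted | Counted |

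The practical loss is in the first two rows. The ethics row hardly changes, since a death judged to be caused by the disease would not be classed as related in either case.

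**Step 2. Ask what separates an exempt death from a reportable one.** The only boundary is the attribution of cause to encephalopathy. The protocol gives no criteria, names nobody to decide, and does not ask for the decision to be made without knowledge of the arm.

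**Step 3. Check the SAE definition.** Section 5.1 requires an SAE to be unexpected. Section 5.3.2 then applies unexpectedness again as a separate test for ethics reporting, defined as "an event that is not listed in the protocol as an expected occurrence". Seriousness and expectedness are separate properties. With both in the definition, a foreseeable death could be argued not to meet section 5.1 at all. The list in section 5.3.2 limits the damage, because it names its events as SAEs without that test.

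**Step 4. Scale.** Inputs: 220 babies (section 3, Study Design); background mortality 28%, range 24 to 38%, in cooled babies with moderate or severe disease (section 1.1); 10% as an assumed lower value. The share of deaths attributed to encephalopathy is not given, so I show an assumed 30 to 90%.

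Deaths = 220 × mortality. Exempt deaths = deaths × share attributed.

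| Mortality | Deaths | Exempt at 30% | 50% | 70% | 90% |
|---|---|---|---|---|---|
| 10% (assumed) | 22.0 | 6.6 | 11.0 | 15.4 | 19.8 |
| 24% | 52.8 | 15.8 | 26.4 | 37.0 | 47.5 |
| 28% | 61.6 | 18.5 | 30.8 | 43.1 | 55.4 |
| 38% | 83.6 | 25.1 | 41.8 | 58.5 | 75.2 |

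**Step 5. Differential attribution, as an illustration only.** Assume equal allocation and 28% mortality in every arm: 61.6 / 3 = 20.5 deaths per arm. If 90% were attributed to the disease in one arm and 70% in another, reported deaths would be 20.5 × 0.10 = 2.1 and 20.5 × 0.30 = 6.2. That is a threefold difference in reported deaths with no difference in mortality.

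**The case against.** The strongest reply is that this is a rule with an exception. The exempting sentence is worded as a qualification, deaths from other causes remain SAEs, and so the list item keeps a meaning. That reading is fair, but it does not remove the difficulty: a deliberate exception still needs a workable boundary, and this one has none.

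Several limits do stand.

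- **A reader might infer that most or nearly all deaths would go unreported as SAEs.** The protocol gives no breakdown of causes of death. Its statement in section 1.1 that the disease is the commonest cause of death in term babies describes a population, not deaths among enrolled babies. The share is unknown.
- **The 28% is not a forecast for this trial.** It is background for moderate or severe disease. Section 4.1 also admits mild cases, although the Study Design section excludes them. The sample size adds only 220 − 3 × 71 = 7 babies for mortality and unusable scans together.
- **A reader might infer that an excess of deaths would be hidden.** The documents do not support this. Adverse events remain reportable, mortality is an outcome, and a death judged to be drug-caused is not exempt. Arrest, intracranial haemorrhage, major thrombosis (other than line-related) and bleeding from coagulopathy are themselves listed SAEs. Nothing restricts the Data Monitoring Committee to SAE forms.
- **A reader might infer that the listed events count as expected and so escape ethics reporting.** No passage labels them as expected; they are called prespecified.
- **A reader might infer that relatedness leaves out the study drugs because section 5.3.2 speaks of research procedures.** The wording can reasonably include the randomised drugs. Naming them would be a drafting preference.

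**Conclusion.** The point holds. Section 5.3.2 either contradicts itself or makes an exception whose boundary is undefined, and both readings let the same death be handled differently by different sites or in different arms. The effect is on the speed and impartiality of safety review. It is not a loss of mortality data, and the primary outcome (thalamic N-acetylaspartate) and its comparison are untouched.

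The size cannot be fixed from the protocol. The total would be about 62 deaths at the background 28% (53 to 84 over the quoted range) and 22 at an assumed 10%. How many would be exempt depends on an attribution share that is not stated. The conclusion does not depend on these figures. It rests on three things that the protocol does state, namely that all Phase 2 babies have the disease, that the arms are known and that death is listed without qualification, and on the absence of any attribution rule.

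The presence of unexpectedness in the section 5.1 definition is a real but secondary wording error.

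**What to change.** 1. In section 5.3.2, delete relapse and death due to neonatal encephalopathy from the exemption. The part on elective hospitalisation can stay. Every death is then an SAE, reported within 24 hours and passed to the Sponsor, whatever its attributed cause. Cause can still be recorded on the form as a description.
2. State that deaths by arm are available to the Data Monitoring Committee.
3. In section 5.1, remove the requirement that an SAE be unexpected, and leave expectedness to the separate ethics-reporting test in section 5.3.2.

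The cost is an amendment to a few lines and the forms for deaths now exempt. On the assumptions above this is roughly 7 forms (10% mortality, 30% attributed) to 55 forms (28% mortality, 90% attributed) over the whole trial, plus a simple tabulation of deaths by arm. The sample size, the outcomes and the analysis do not change.
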